#### Modified ITT (mITT) Patient Identification Data Review Process

- Step 1. Statistical programmer programs to create excel file, which is a list of patients who will be excluded from ITT population due to lack of mUFC data at week 12. Send this excel file to DML.
- Step 2. Based on the list of patients in above excel file, DM team will track all the possible reasons why patients did not have mUFC data at week 12 for each patient.
- Step 3. Get the information of reasons for no mUFC data at week 12 from DML, draft data review report.
- Step 4. Send the drafted data review report to Recordati for review.
- Step 5. Get the review comments from Recordati, discuss the review comments in comments resolution meeting.

The above data review process will also be applied to the missing mUFC data at the baseline.

Project Document Version No.: 4.0; Document Effective Date: 30 October 2023

CONFIDENTIAL

TP-GDO-WW-096-09 Effective Date: 22 Dec 21

Related to: SOP-GDO-WW-019 Page 14 of 31

### **On-Treatment Population**

The On-Treatment population consists of all participants while they are taking osilodrostat at a defined timepoint or period.

- In circumstances where end of treatment date is missing and patient did not change to 0mg prior
  to end of study, the end of study date will be considered as end of treatment date if end of study
  reasons were due to adverse event, death, osilodrostat permanently discontinued, administrative
  reasons (no data reported), end of retrospective follow-up period.
- For cases where last recorded dose was changed to 0mg prior to the end of study, then the date
  when dose changed to 0mg will be considered as the last date of exposure (i.e., end of treatment
  date).

#### **Safety Population**

The Safety population consists of all participants who receive at least one dose of osilodrostat.

Safety analysis will be performed on the Safety population.

Decisions regarding the exclusion of participants and/or participant data from analyses will be made prior to the Database lock (DBL) during the data review meeting and will be documented and approved by Recordati.

The number and percentage of patients included and excluded from each analysis population, along with reasons for exclusion, will be summarized.

A listing of participants included in each analysis population will also be provided. Participants exclusion from analysis sets will be listed with reasons for exclusions.

## 3.4 Study Groups/Cohorts

This is retrospective, observational single-cohort study with up to 36 months of retrospective real-world data review period.

#### 3.5 Definitions of Subgroup Indicators

The following subgroup analyses will be performed.

#### Type of interventions

The participants will be classified according to the interventions they received:

- 1) *Tx naïve*: All patients who were treated with Osilodrostat as monotherapy that were not taking any medical therapy for Cushing's syndrome prior to the start of Osilodrostat (limited to somatostatin analogues, dopaminergic medications, and steroidogenesis inhibitors)
- Switch group: All patients who were treated with Osilodrostat as monotherapy but were taking any medical therapy for Cushing's syndrome and discontinued these prior to the start of Osilodrostat.
- 3) **Combination Tx**: All patients treated with both Osilodrostat and any medical therapy for Cushing's syndrome.

Project Document Version No.: 4.0; Document Effective Date: 30 October 2023

**CONFIDENTIAL** 

#### Method of Osilodrostat use/ titration

The participants will be classified as follows:

- 1) **Block-and-replace:** Patients who are taking glucocorticoids as concomitant medication less than 2 weeks after initial Osilodrostat.
- 2) *Initial titration followed by block-and-replace:* Patients who initiated Osilodrostat and after at least 2 weeks, started taking glucocorticoids as concomitant medication.
- Titration only: Patients who did not take glucocorticoids as concomitant medications while taking osilodrostat

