LINC 3 was a 4-period prospective, multicentre, open-label, phase III study with a double-blind randomised withdrawal period, which studied osilodrostat in 137 adults with confirmed persistent or de novo CD. Participants were initiated and treated to target mean UFC (mUFC) with open-label osilodrostat during Weeks 1 to 12, continued on a therapeutic dose of osilodrostat during weeks 13-24; eligible patients were randomised to either continue osilodrostat or switch to matching-placebo at Week 26 until Week 34, and then given open-label osilodrostat from Week 34 until study end at Week 48 whereas non—eligible patients continued open-label osilodrostat until the end of the core phase. At Week 34, maintenance of complete response was found in more patients in the osilodrostat group compared with the placebo group (31 [86%] vs 10 [29%]; odds ratio 13.7 [95% CI 3.7-53.4]; p<0.0001). At Week 24, The proportion of patients with normal mUFC at week 24 is 93/137 (67.9) (CI (59.37, 75.60). Nausea (57/137 [42%]), headache (46/137 [34%]), fatigue (39/137 [28%]), and adrenal insufficiency (38/137 [28%]) were the most common adverse events (AEs) (i.e., occurred in >25% of participants). Hypocortisolism-related AE were observed in (51%; n=70) and adrenal hormone precursors-related AE in (42%; n=58) of study patients. Also, other adverse events included anemia (8%), hypokalaemia (18 [13%]) and hypertension (17 [12%]). Non-serious cardiac adverse events included QT interval prolongation in five (4%) patients and pituitary adverse events included pituitary tumour enlargement, pituitary tumour volume increase, increased adenoma size, or pituitary tumour growth in four (3%) patients. This trial demonstrated adequate safety and efficacy of osilodrostat in patients with CD (Pivonello et al. 2020).

Final v2.0 28 of 63 18 April 2023

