#### 5.3.3.11 Proportion of participants who experienced TEAE and AESI

A treatment-emergent adverse event (TEAE) is defined as an AE that begins or that worsens in severity after at least one dose of osilodrostat has been administered. The start date of adverse events will be compared with date of first dose of osilodrostat and the date of the earlier of loss to follow-up, death, the end of the retrospective follow-up period or treatment discontinuation occurs, whichever is earlier.

TEAE will be coded according to the latest Medical Dictionary for Regulatory Activities (MedDRA) terms and summarized by MedDRA System Organ Class (SOC) and Preferred Term.

Adverse Events of Special Interest (AESI) will be defined as following AEs:

- Adrenal hormone precursor accumulation-related AEs
- Hypocortisolism-related AEs
- Pituitary tumour enlargement-related AEs
- Arrhythmogenic potential and QT prolongation AEs

All AEs will be assessed according to incidence, grade, causality, outcome, action taken and seriousness. The details are provided in the safety analysis section 5.10.1 below.

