#### 5.8 Prior and Concomitant Medications

The prior and concomitant systemic therapy, radiotherapy and surgical therapy will be summarized in similar manner as described.

Medication start and stop dates will be compared to the date of first dose of osilodrostat to allow medications to be classified as either Prior only, both Prior and Concomitant, or Concomitant only. Medications starting after the completion/withdrawal date will be listed but will not be classified or summarized.

Medications that start and stop prior to the date of first dose of osilodrostat will be classified as Prior only. If a medication starts before the date of first dose of osilodrostat and stops on or after the date of first dose of osilodrostat, then the medication will be classified as both Prior and Concomitant. Medications will be classified as Concomitant only if they have a start date on or after the date of first dose of osilodrostat.

If medication start and/or stop dates are missing or partial, the dates will be compared as far as possible with the date of first dose of osilodrostat (see section 5.11.2). Medications will be assumed to be Concomitant only, unless there is clear evidence (through comparison of partial dates) to suggest that the medication started prior to the first dose of osilodrostat. If there is clear evidence, such as an ongoing medical history with the same indication, to suggest that the medication started prior to first dose of osilodrostat and with no stop date, the medication will be assumed to be both Prior and Concomitant. If there is clear evidence to suggest that the medication stopped prior to first dose of osilodrostat, the medication will be assumed to be Prior only.

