#### 5.10 Subgroup Analysis

- i) Selected demographics and patient exposure by subgroups
  - (1) Patient disposition
  - (2) Summary of demographic and baseline disease characteristics
  - (3) Concomitant medications
  - (4) Summary of duration of exposure to Osilodrostat
  - (5) Summary of dose change from initial dose by visits
- ii) Selected efficacy endpoints by subgroups
  - (1) Proportion of mUFC response by (week 4 to 60) mITT and On-treatment population
  - (2) Change in mUFC from baseline by visits in mITT and On-treatment population
  - (3) Proportion of salivary cortisol response by (week 4 to 60) mITT and On-treatment population
  - (4) Proportion of composite measures of cortisol level response by (week 4 to 60) mITT and On-treatment population
  - (5) Change in serum cortisol from baseline by visits in mITT and On-treatment population.
- iii) Selected safety endpoints by subgroups
  - (1) Overview of adverse events
  - (2) Summary of adverse events of special interests by system organ class and preferred term

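### The titration-method groups count any concomitant glucocorticoid whatever its indication, so the AESI table by method understates hypocortisolism under titration only and overstates it under block-and-replace

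*SAP*

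**What the plan says.** SAP Section 3.5, under the heading on method of osilodrostat use, sets three groups:

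- Group 1, *Block-and-replace*: "Patients who are taking glucocorticoids as concomitant medication less than 2 weeks after initial Osilodrostat".
- Group 2, *Initial titration followed by block-and-replace*: "Patients who initiated Osilodrostat and after at least 2 weeks, started taking glucocorticoids as concomitant medication".
- Group 3, *Titration only*: "Patients who did not take glucocorticoids as concomitant medications while taking osilodrostat".

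Neither block-and-replace group refers to indication, planned replacement or duration. Only group 3 requires the patient to be on osilodrostat at the time.

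SAP Section 5.8 defines concomitant by dates alone: "Medications will be classified as Concomitant only if they have a start date on or after the date of first dose of osilodrostat". It also sets a cut-off: "Medications starting after the completion/withdrawal date will be listed but will not be classified or summarized". It does not say whether that date refers to the study or to treatment.

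SAP Section 5.3.3.11 lists "Hypocortisolism-related AEs" among four AESI categories. The safety part of SAP Section 5.10 plans, by subgroup, a "Summary of adverse events of special interests by system organ class and preferred term". SAP Section 5.9.1 separately plans an AESI summary for the whole Safety population.

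**The concern.** The groups are meant to describe how osilodrostat was used. The rule instead reacts to something that happens during follow-up and can be a direct consequence of the outcome being tabulated. If hypocortisolism is treated with a glucocorticoid, that treatment decides the column in which the event is counted, so the comparison by method is partly circular.

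How the drug is dosed and titrated is a stated research question (Protocol Section 7), and the study is meant to support a supplemental application. A reader of the subgroup table could take a difference between methods as information about their relative safety when the labelling rule produced some or all of it.

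**Working it through.** **Figure to reproduce.** The documents give no rate or sample size for these subgroups, so there is no design figure to reproduce. What follows is an illustration of the rule.

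**Inputs**
- p, the hypocortisolism rate among titrated patients: 70/137 = 51.1%, the hypocortisolism-related event rate that Protocol Section 6 reports from the earlier phase III trial in Cushing's disease. This is the same category as the AESI. Carrying it over to this population is an assumption.
- g, the share of those cases given a glucocorticoid: not in the documents. Range shown: 25% to 100%.

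**Rate shown for *Titration only*.** Of all titrated patients a fraction p·g is relabelled, and every one of them has the event. What remains is

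shown rate = p(1 − g) / (1 − p·g).

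For g = 0.50: 0.511 × 0.50 = 0.255, and 0.255 / (1 − 0.255) = 34.3%.

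| g | Relabelled per 100 titrated | *Titration only* shows | Without relabelling |
|---|---|---|---|
| 25% | 12.8 | 43.9% | 51.1% |
| 50% | 25.5 | 34.3% | 51.1% |
| 75% | 38.3 | 20.7% | 51.1% |
| 100% | 51.1 | 0% | 51.1% |

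**Rate shown for group 2.** Take 100 patients, of whom b are on planned block-and-replace with the same p. Assume that all relabelled patients enter group 2:

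shown rate = [b·p + (100 − b)·p·g] / [b + (100 − b)·p·g].

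At g = 0.50:
- b = 0: 100%
- b = 10: 85.2%
- b = 20: (10.2 + 20.4) / (20 + 20.4) = 75.8%
- b = 30: 69.4%

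*Titration only* stays at 34.3% in each case, and the overall rate stays at 51.1%. The true rates were set equal, so the whole gap comes from the rule.

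**Other values of p.** Protocol Section 6 also gives adrenal insufficiency, a single term and so a looser match to the AESI. For g = 25%, 50%, 75% and 100%:
- 38/137 = 27.7%, same trial: 22.4%, 16.1%, 8.8% and 0%.
- 7/9 = 77.8%, the nine-patient non-CD study: 72.4%, 63.6%, 46.7% and 0%.

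**Group 1.** It has the same gap. A glucocorticoid given for hypocortisolism within the first 2 weeks puts the patient there. So does one whose start and end dates are both missing, because SAP Section 5.11.2 then sets the start to the first osilodrostat dose.

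**Overlap of groups 2 and 3.** The On-Treatment definition in SAP Section 3.3 allows the dose to reach 0 mg before the end of study. A glucocorticoid started in that interval, at 2 weeks or later, is concomitant by date and so meets group 2. If none was taken while on osilodrostat, the patient also meets group 3. Whether this can happen depends on how the cut-off date in SAP Section 5.8 is read.

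**The case against.** Several counter-arguments have force.

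**Nothing is lost.** A reader might infer that the table hides hypocortisolism. It does not: treated cases move to a block-and-replace column and remain in the overall AESI summary, which answers the stated incidence objective. Cases managed without a glucocorticoid stay in *Titration only*. What stands is the distortion between columns.

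**The size is unknown.** A reader might also infer that titration alone will look almost free of hypocortisolism. That requires nearly all cases to be treated with a glucocorticoid, and the documents do not give this share. At half treated, the shown rate is still 34%.

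**Medication after stopping.** It is tempting to say that a glucocorticoid started after osilodrostat ends makes the patient block-and-replace. The text does not go that far. Such a patient can meet two definitions, and the SAP does not say which prevails. Follow-up ends at treatment discontinuation (SAP Section 3), and if the cut-off in SAP Section 5.8 means treatment withdrawal, the overlap largely closes.

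**The study is descriptive.** No test or formal comparison of methods is planned, and one subgroup safety table is the main output affected. This limits the consequence, but a descriptive rate can still be biased.

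**Intent is hard to judge from charts.** This is fair. A patient who starts a glucocorticoid for an adverse event and continues both drugs would sit in *Titration only* against that group's own wording if simply kept there. The remedy must not rest on intent alone.

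**Conclusion.** The concern holds as a bias in one planned table. Nothing in the SAP stops treatment of hypocortisolism from changing the group in which the event is counted. The direction is fixed whenever any such case in a titrated patient is treated with a glucocorticoid: *Titration only* too low, block-and-replace too high. With p = 51%, *Titration only* shows between 44% (a quarter treated) and 0% (all treated). These sizes rest on a rate carried over from Cushing's disease and on an assumed treated share. The overall AESI rate does not change.

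The overlap between groups 2 and 3 is a secondary ambiguity of wording, to be reconciled with the cut-off in SAP Section 5.8. It is not a demonstrated misassignment. The point merits correction before database lock; it does not touch the primary analysis.

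**What to change.** 1. In SAP Section 3.5, apply one on-treatment condition (glucocorticoid taken while the osilodrostat dose is above 0 mg) to all three groups. Let the first such glucocorticoid decide between groups 1 and 2, so that the groups are mutually exclusive. State in Section 5.8 which date the completion/withdrawal cut-off means.
2. For the AESI table by method, do not let a glucocorticoid recorded as treatment for an adverse event change the group. Flag these patients and show them as a separate row.
3. Also present hypocortisolism AESIs with onset before the first glucocorticoid, by the method in use at onset. This uses dates only and needs no judgement of intent. State the denominator (patients who began osilodrostat without a glucocorticoid) and a rule for equal dates. Ties are likely, because SAP Section 5.11.2 imputes partial adverse-event and medication dates by the same rule.

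The cost is SAP wording, one derived flag, one more table, and review before lock of records whose indication is unclear. The data review meeting in SAP Section 3.3 could take the review. The number of such records cannot be judged from the documents.

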#### Reason for Osilodrostat use

- 1) **Short-term use in preparation for surgery**: Patients who took Osilodrostat for < 12 weeks had a surgical procedure to treat Cushing's syndrome and were not restarted on Osilodrostat.
- 2) Chronic use: All other patients

#### Type of non-CD Cushing Syndrome

- 1) ACTH-dependent CS: Patients classified as "Ectopic Adrenocorticotropic Hormone Secretion" in the "CS Disease Causation".
- 2) Adrenal CS: Patients with "Adrenal Adenoma", "Adrenocortical Carcinoma" in the "CS Disease Causation".
- 3) Unclassified: "Adrenal hyperplasia" and "Other" in the "CS Disease Causation".

# 3.6 Study Endpoints

#### 3.6.1 Primary Endpoint

The primary endpoint is:

a) Number and proportion of participants with mean urinary free cortisol (mUFC) ≤ upper limit of normal (ULN) at 12 weeks.

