#### Inclusion criteria:

- Male and female patients ≥18 years old with diagnosis of CS, except for CD (i.e., an aetiology of adrenal adenoma, adrenocortical carcinoma, adrenal hyperplasia, or ectopic adrenocorticotropic hormone secretion). Patients should have a contemporaneously documented diagnosis of CS as per effective guidelines.
- 2) Patients treated with osilodrostat between April 2019 and study start date (16 December 2022) as part of ATU programme or commercialisation.

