#### Exclusion criteria:

- 1) Patients who participated in an interventional clinical trial anytime during the study period.
- 2) Patients with Pseudo-Cushing's syndrome, cyclic CS, or iatrogenic CS.

As this is a retrospective, non-interventional study, no specific withdrawal and replacement criteria are specified.

Project Document Version No.: 4.0; Document Effective Date: 30 October 2023

CONFIDENTIAL

TP-GDO-WW-096-09 Effective Date: 22 Dec 21

Related to: SOP-GDO-WW-019 Page 13 of 31

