## 3.3 Primary Analysis Population

#### **ITT Population**

The Intent-to-treat population (ITT) consists of all enrolled participants who, have met all inclusion/exclusion criteria and have received osilodrostat treatment for non-CD CS, with a potential follow-up of at least 12 weeks. The only patients excluded from the primary efficacy analyses will be the ones who started treatment with osilodrostat less than 12 weeks prior to the end of the abstraction period and are still treated with osilodrostat at the end of the abstraction period. These patients will be included only in the analyses of the secondary and exploratory endpoints including safety.

All effectiveness analysis will be performed on the ITT population.

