# 3.6.3 Exploratory endpoint(s)

The exploratory effectiveness endpoint is:

- a) Proportion of participants with normal late night salivary cortisol at Week 4, 8, 12, 18, 24, 36, and at every 12 weeks until the earlier of loss to follow-up, death, or the end of the retrospective follow-up period or treatment discontinuation
- b) On-treatment analysis of cortisol levels
  - a. Normalization of cortisol measures at Week 4, 8, 12, 18, 24, 36, and at every 12 weeks until the earlier of loss to follow-up, death, or the end of the retrospective follow-up period or treatment discontinuation (mUFC, salivary cortisol and serum cortisol and a combination of the 3 measures). Participants with normal values at baseline would not enter in this analisis.
  - b. Composite of normalization of week 12 cortisol measures: For patients taking Osilodrostat on week 12 (mUFC, salivary cortisol and morning serum and a combination of the 3 measures).
  - c. Normalization to the last on treatment cortisol measures (mUFC, salivary cortisol and morning serum and a combination of the 3 measures).
  - d. Patients with normalization of the majority of cortisol measures: Defined as patients on Osilodrostat treatment that have multiple measures of cortisol levels over time and have >50% of these measures ≤ ULN (mUFC, salivary cortisol and morning serum and a combination of the 3 measures).
  - e. Change from baseline of measures cortisol level: Defined as the change from baseline in measures of cortisol levels including only patients receiving Osilodrostat the time-point (expressed by the unit and bx nfold ULN) for mUFC, salivary cortisol and morning serum and a combination of the 3 measures.
  - f. Complete or partial responders: The proportion of patients with normalization of cortisol levels or a ≥50% reduction from baseline for patients receiving Osilodrostat at week 4, 8, 12, 18, 24, 36, and at every 12 weeks until the earlier of loss to follow-up, death, or the end of the retrospective follow-up period or treatment discontinuation (mUFC, salivary cortisol and morning serum and a combination of the 3 measures).
  - g. Waterfall plot figures of change in measures of cortisol level from baseline to last on treatment expressed as n-fold ULN (mUFC, salivary cortisol and morning serum and a combination of the 3 measures) grouped by duration of exposure to osilodrostat (0 to 4 weeks, 5 to 8 weeks, 9 to 12 weeks, 13 to 24 weeks, >24 weeks).

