#### 5.3.2 Analysis of the Primary Endpoint

The mean UFC for a participant at any particular visit is collected in the site. If mean UFC is not available at that visit, the mean UFC will be computed based on two or more individual 24hr UFC specimens at that visit. If there are only one individual 24hr UFC specimen available at that visit, then this one individual 24hr UFC specimen will be considered as mean UFC with the acknowledgement of clinical practice in France where one 24 hours UFC can inform on clinical decision.

The primary endpoint is the number and proportion of participants with mUFC ≤ ULN at 12 weeks will be summarized descriptively along with associated 95% CI. The participants who discontinued treatment prior to 12 weeks for any reason or were lost-to-follow up will be considered non-responders for the primary endpoint. The participants who started treatment with osilodrostat less than 12 weeks prior to the end of the abstraction period and are still treated with osilodrostat at the end of the abstraction period will be excluded from the analysis.

Project Document Version No.: 4.0; Document Effective Date: 30 October 2023

CONFIDENTIAL

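### The 2-week baseline definition contradicts the 1-month mUFC exception in the footnotes; time to normalization does not require an elevated start, and one ITT table by baseline mUFC status would help

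*SAP*

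**What the plan says.** **Baseline window.** SAP 5.2 (General Presentation Considerations) and Protocol 8.7.9 define baseline as the value at osilodrostat initiation or the nearest one in the 2 weeks before it. Neither makes an exception. SAP 5.2 adds that change and percent change are not calculated when a variable has no baseline value. Under the data collection schedules (SAP Table 1, Protocol Table 2), footnote f lets baseline mUFC come from up to 1 month before initiation. Footnote g says the 2-week footnote does not apply to mUFC.

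**Time to normalization.** SAP 5.3.3.10 measures from the start of osilodrostat to normalization and censors the rest at the last cortisol measure. It sets no condition on the starting value. For the composite, baseline is whichever cortisol measure lies nearest to the start, with no window stated.

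**Primary endpoint and population.** The endpoint in SAP 3.6.1 is a Week-12 status: "Number and proportion of participants with mean urinary free cortisol (mUFC) ≤ upper limit of normal (ULN) at 12 weeks". Eligibility asks for a diagnosis: "Patients should have a contemporaneously documented diagnosis of CS as per effective guidelines". The ITT set takes patients who "have received osilodrostat treatment for non-CD CS, with a potential follow-up of at least 12 weeks". Neither requires mUFC above ULN at the start. SAP 3.5 recognises a switch group and a combination group ("All patients treated with both Osilodrostat and any medical therapy for" Cushing's syndrome). Under SAP 5.3.2, "The participants who discontinued treatment prior to 12 weeks for any reason or were lost-to-follow up will be considered non-responders for the primary endpoint".

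**Where baseline normality is used.** Item b.a of SAP 3.6.3, an on-treatment exploratory analysis, states: "Participants with normal values at baseline would not enter in this analisis". SAP 5.3.5 also runs the primary endpoint on the On-Treatment population.

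**The concern.** The two baseline rules cannot both be programmed. An mUFC value taken three weeks before the first dose is a baseline under footnotes f and g and missing under SAP 5.2. The choice decides who contributes to mUFC change from baseline and to partial response, whom item b.a removes, and who enters the missing-baseline review in SAP 3.3.

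In the time-to-normalization analysis, a patient already at or below ULN has nothing to normalize. Read literally, that patient still counts as an event at the first normal value after the start, which shortens the Kaplan-Meier median.

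The third matter is one of interpretation. This is a single-arm study meant to support a label expansion, so readers may take the Week-12 proportion as normalization under osilodrostat. Part of it may be control already present at the start. Excluding "cyclic CS, or iatrogenic CS" closes one route to a normal baseline, but not the route through earlier or concurrent cortisol-lowering drugs. That SAP 3.6.3 excludes baseline-normal patients from one analysis shows that the plan expects some.

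**Working it through.** **1. Baseline window: the passages side by side**

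| mUFC value dated | SAP 5.2, Protocol 8.7.9 | Footnotes f and g, both documents |
|---|---|---|
| Initiation to 2 weeks before | baseline | baseline |
| 2 weeks to 1 month before | missing | baseline |
| More than 1 month before | missing | missing |

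Only the middle row conflicts. The primary count uses no baseline value, so it does not change. The documents do not say how many values fall in that row. If a share g of evaluable baselines did (assumed), the standard error of the mean mUFC change would grow by 1/√(1 − g), other things equal:

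- g = 10%: 1.05
- g = 25%: 1.15
- g = 50%: 1.41

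**2. Time to normalization**

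Assume 100 patients, no censoring, and all baseline-normal patients counted as events at their first post-start measure, before the others. The overall median is reached at 50 events.

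- 10 baseline-normal: 40 of the 90 elevated patients have normalized (44.4%).
- 20 baseline-normal: 30 of 80 (37.5%).

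The reported median is therefore earlier than the median among elevated patients.

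**3. Week-12 rate by baseline status**

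*Method check.* SAP 5.2 specifies Clopper-Pearson intervals. For the 93/137 in Protocol section 6 the method gives 67.9% (59.37 to 75.60), as printed there. The study size of approximately 100 rests on practical grounds, so there is no sample-size figure to reproduce.

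*Inputs.* N = 100 (SAP 5.12). Overall rate p = 67%, assumed; the only non-CD anchor is 6/9 in the Japanese study (Protocol section 6), exact interval 29.9 to 92.5%. The baseline-normal share f and that group's Week-12 rate r are not given and are assumed.

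*Formula.* All-ITT rate minus baseline-elevated rate = f(r − p)/(1 − f), in points:

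| f | r = 20% | r = 50% | r = 100% |
|---|---|---|---|
| 5% | −2.5 | −0.9 | +1.7 |
| 10% | −5.2 | −1.9 | +3.7 |
| 20% | −11.8 | −4.3 | +8.3 |

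At f = 20% the elevated group is 63/80 = 78.8% (68.2 to 87.1) when r = 20%, and 47/80 = 58.8% (47.2 to 69.7) when r = 100%. The overall 67/100 has interval 56.9 to 76.1, half-width 9.6 points. The gap passes 9.6 points near f = 17% at r = 20%, and near f = 22.5% at r = 100%.

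*What the planned on-treatment contrast shows.* Take 67 responders, 16 baseline-normal patients and 15 elevated early stoppers, with a Week-12 mUFC for everyone still treated (all assumed).

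- 14 of 16 respond. The ITT gap is 67.0 − 53/84 (63.1) = +3.9. With no baseline-normal early stopper, the contrast is 67/85 − 53/69 = 78.8 − 76.8 = +2.0. With two it is +3.9.
- 8 of 16 respond. The ITT gap is 67.0 − 59/84 (70.2) = −3.2. The contrast is 67/(85 − s) − 59/69, where s is the number of baseline-normal early stoppers. It is −6.7 at s = 0, −0.7 at s = 6, +0.4 at s = 7 and +1.5 at s = 8.

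The contrast usually gives the direction. Its size, and at the extreme its sign, depends on baseline-normal early stoppers, who are ITT non-responders but leave the On-Treatment set.

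**The case against.** **On the window.** Footnote g expressly lifts the 2-week rule for mUFC, and the amendment log describes the footnotes as clarifications. An analyst who lets the specific rule override the general one would keep the 1-month values. That makes the intention fairly clear. It does not settle the text, because the analysis definition in SAP 5.2 carries no exception and Protocol 8.7.9 repeats it. A reader might infer that many baselines would be lost; the documents do not give the number, and the shares used above are assumptions.

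**On the ITT split.** The study is descriptive and the endpoint is a validly defined status. Besides item b.a and the On-Treatment run, the plan has change from baseline in multiples of ULN, an ITT stratification by other CS therapy (SAP 5.3.6), mUFC response by switch and combination group (SAP 5.10) and a patient-level listing (SAP 5.3.2). Most of this stands, so the table is an improvement and not the repair of an error. What remains is that none of these tabulates the ITT Week-12 proportion by baseline mUFC. The subgroup efficacy outputs use the mITT and On-Treatment sets. Shift tables are either unspecified (SAP 5.2) or run to the worst or last value (SAP 5.9.3).

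**Stronger readings to avoid.** A reader might infer that the primary rate is invalid or inflated. The documents do not support this: the sign depends on the Week-12 rate of baseline-normal patients, and early stoppers among them pull the rate down. Nor can one say that the gap must stay inside the interval half-width, since that depends on an assumed floor for the same rate.

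**Conclusion.** The baseline window is wrong as written: the text definitions in both documents conflict with footnotes f and g in both documents. The conflict touches every mUFC analysis that uses a baseline, and not the primary count. This conclusion needs no assumption; only the number of patients affected is unknown.

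Time to normalization is incompletely specified. Taken literally it counts already-normal patients as events and shortens the median, by an amount that depends on the unreported baseline-normal share. The composite baseline has no window.

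The missing ITT split is a lesser matter. The Week-12 rate can mix normalization with maintained control, and the planned on-treatment contrast addresses this only for patients still treated. The range of −11.8 to +8.3 points rests on an assumed 67% overall rate, an assumed 20% baseline-normal share and assumed rates of 20% to 100% in that group. It illustrates that the shift could go either way and does not estimate it.

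**What to change.** 1. **SAP 5.2.** Add that for mUFC the baseline is the value nearest to initiation within the month before it, in line with footnote f. Use this in every mUFC analysis that needs a baseline, and record the difference from Protocol 8.7.9 in SAP 5.13. Protocol 8.7 asks for an amendment only when a principal feature changes. Cost: one sentence and one entry.
2. **SAP 5.3.3.10.** Restrict the analysis to patients with a baseline above ULN for the measure analysed. Report how many are left out as at or below ULN and how many for a missing baseline. Apply the SAP 5.2 windows to the composite baseline. Cost: fewer patients.
3. **SAP 5.3.2.** Keep the all-ITT primary. Add one supportive table of the ITT Week-12 proportion with exact 95% interval by baseline mUFC (above ULN, at or below ULN, missing), using the primary denominator. Show in each row the number still treated without a Week-12 mUFC, because the non-responder rule covers only discontinuation and loss to follow-up, and SAP 5.11.1 replaces no missing data.

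The table needs no new data. Its intervals are wider: half-width about 10.2 to 11.5 points for 90 to 70 patients near a 67% rate, against 9.6 for 100. The row at or below ULN is imprecise: about 18 points at 14/16 and 25 at 8/16. Selecting on an elevated baseline also brings some regression to the mean, more so where a single specimen serves ("then this one individual 24hr UFC specimen will be considered as mean UFC"). For these reasons the table should stay supportive.
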